1_4	06_02_2019	[name]	
 - Addition that reminder texts will be optional and removal of reminder texts for healthy ageing intervention. - Statement added to say Phonak is the hearing aid provider and Way With Words will be used to transcribe the qualitative interviews. - Relax inclusion criteria from 'MCI diagnosed or confirmed in the last 12 months' to 'clinical diagnosis of MCI'. - Change in audiometric hearing impairment criterion to 'Participants must have adult-onset hearing impairment with a four-frequency pure tone average (0.5, 1, 2, 4 kHz) in the better-hearing ear of ≥ 25 decibels Hearing Level (dB HL) and <70 dB HL or a pure tone audiometric threshold at 4 KHz in the better ear of ≥ 30 decibels dB HL and <70 dB HL' - Change in exclusion criteria from 'Any self-reported hearing aid use in the past year' to 'potential participants who have already been prescribed hearing aids in the past will be excluded if they report any hearing aid use within the past month. Temporary exclusion: Potential participants will also be excluded if their hearing aids were prescribed in the past three months, irrespective of their use; however, we will contact these potential participants again after 3 months following prescription of their hearing aids and they will be eligible if they have not used their hearing aids in the past month' - Relax exclusion criterion 'Unwillingness or inability, in the opinion of the researchers, to complete trial procedures and/or wear hearing aids on a daily or near daily basis' by removing the additional text that expanded on this criterion. - Correction of incorrect statement in 'Planned recruitment rate' section. 'We conducted a small (n=12) feasibility study with the same inclusion and exclusion criteria as the proposed trial' changed to 'We conducted a small (n=12) feasibility study with similar but less restrictive inclusion and exclusion criteria as the proposed trial.'
-----	------------	--------------------	--

1_5	21_10_2019	[name]/[name]	
 - In the Section '2 Summary', we have corrected the title of the trial which had erroneously included "single blind" as this is, in fact, an open label trial. - In the Section '2 Summary', we have corrected the duration from a '12 week' to a '6 week' intervention as the longer duration was introduced in error. - Under section '2 Summary' of the protocol, we have corrected the criteria based on the approved substantial amendment 1 which removed the need for MCI to be diagnosed in the last 12 months, and allowed inclusion of participants with no use of hearing aids in the last month (rather than the last year). - Under section 4 of the protocol, titled 'Objectives', we have moved the objective to 'estimate the difference in adherence to hearing aid between the arms' from a primary objective to a secondary objective. - We updated the inclusion criterion (Section 6.1) for audiometric hearing impairment to remove the upper limit for potential participants included because of a pure tone audiometric threshold at 4 KHz in the better ear of ≥ 30 decibels dB HL. - We updated the eligibility criteria (Section 6.1) to include people who have 'low use' of hearing aids, rather than only those who report no use in the last month. - We have changed the wording for the audiological onwards medical referral criteria. - In point 8 of the exclusion criteria (Section 6.2), we have expanded the ways in which we will advise participants how to get their cerumen removed. - Under section 7 of the protocol, titled 'Informed consent', we have added a paragraph to explain how we will adapt the informed consent process for those who are physically unable to sign the informed consent form. - We have added the 'Questionnaire on need for help for hearing aid use' to the protocol under Session A and Session C of the Healthy Ageing intervention (Section 8.3) as this is missing in error. - We have removed the repeated C2Hear video shown at Visit 3 Session B. - Update to say that either the audiologist or research assistant can conduct Session A and
-----	------------	--	---

			
Session C of the hearing intervention instead of research assistant only.
 
 - Update to say we will replace up to two pairs of hearing aids instead of only replacing once. - Change to the definition of the primary outcome relating to recruitment and randomisation. - Change to wording for the secondary outcome related to timely hearing aid fitting. - Under the section '11. Statistical Considerations' and '11.6 Statistical analysis', we have unified the primary and secondary outcomes regarding hearing aid use. - Change to the outcome measure definition for the comparison of hearing aid use between the two intervention arms. - We added a statement to say we will contact participants via a third party software called 'GreenText'.
1_6	15_07_2020	[name]/[name]	
Substantial amendment with protocol changes for the Remote Hearing Intervention (RHI) sub-study during COVID-19:
 
 - Section 2.Summary: to summarise protocol changes - Section 3.Background: providing rationale for RHI sub-study. - Section 3.1. Assessment of risk: measures to ensure safety and prevent exposure to COVID-19 during RHI sub-study. - Section 4. Objectives: updated with the objectives for the RHI sub-study - Section 5: Design. Updated to include design description for RHI sub-study during COVID-19 - Section 6: Selection of participants: updated with eligibility criteria, recruitment and consent procedures for the RHI sub-study - Section 7: added description of the RHI. - Section 8: description of RHI procedures and data collection - Section 11: added outcomes specific to RHI. - Added Appendix 2. Schedule of assessments for the Remote Hearing Intervention sub-study (during COVID-19) 
Other minor change to protocol outside of RHI sub-study changes:
 
 - Removal of Likert scale measuring acceptability of the interventions during qualitative

			
interviews and added to the list of assessments at Session D for the original TACT pilot trial. This was approved to be asked at Session D but the protocol has not been amended to reflect this, we now wish to correct this error.

--	--	--	---

Contents

Protocol Version History	2
List of abbreviations	11
1 Trial personnel	12
2 Summary.....	13
3 Background and Rationale	14
3.1 Assessment and Management of Risk	16
4 Objectives	20
5 Trial design.....	20
6 Selection of Participants	24
6.1 Eligibility criteria.....	24

CRO	Contract Research Organisation
DMC	Data Monitoring Committee
GAfREC	Governance Arrangements for NHS Research Ethics
GCP	Good Clinical Practice
HTA	Human Tissue Authority
IB	Investigator’s Brochure
ICF	Informed Consent Form
IDMC	Independent Data Monitoring Committee
IMP	Investigational Medicinal Product
ISF	Investigator Site File
ISRCTN	International Standard Randomised Controlled Trial Number
NHS R&D	National Health Service Research & Development
PI	Principal Investigator
PIS	Participant Information Sheet
QA	Quality Assurance
QC	Quality Control
RCT	Randomised Controlled Trial
REC	Research Ethics Committee
SAE	Serious Adverse Event
SDV	Source Document Verification
SOP	Standard Operating Procedure
SPC	Summary of Product Characteristics
TMG	Trial Management Group
TSC	Trial Steering Committee

1 Trial personnel

See protocol cover page for Chief Investigator and Sponsor contact details.

Statisticians	[name] Department of Statistical Science University College London Email: [contact] Tel: [contact] [name] Department of Statistical Science, UCL Email: [contact]
Co-Investigators	[name], Ear Institute, UCL [name], Ear Institute, UCL [name], Division of Psychiatry, UCL [name], Division of Psychiatry, UCL
Collaborators	[name], Cochlear Center for Hearing and Public Health, Johns Hopkins
Trial Manager	[name], Division of Psychiatry, UCL [contact]
Research Assistants	[name] [contact] [name] [contact] [name] [contact]
Trial Audiologist	[name] [contact]
Research support service	Noclor [name]

2 Summary

Objectives:	To establish the feasibility of a future fully powered trial of early hearing aid provision in people with Mild Cognitive Impairment (MCI) and hearing loss in terms of delaying the onset of dementia. The pilot trial will test recruitment, attrition, and acceptability of two interventions: the hearing and healthy ageing interventions. During the COVID-19 pandemic, the trial will instead pilot a remotely delivered version of the active intervention of early hearing aid provision and support to test recruitment, feasibility and acceptability (the Remote Hearing Intervention or RHI sub-study).
Type of trial:	
TACT is a pilot randomised, parallel group trial in participants with MCI and hearing loss.
 
During the COVID-19 pandemic, the RHI sub-study will be a single-arm, non-randomised trial in the same participant population.

Trial design and methods:	
For TACT, participants with hearing loss and MCI will be randomised to a hearing intervention (home-based provision of hearing aids, and adherence support delivered over a 6 week intervention) or a healthy ageing intervention (home-based educational intervention, to match intensity of social contact). Participants will be assessed on their hearing, quality of life, physical activity, mood, social interactions, and daily function at baseline and 6 months.
 
During the COVID-19 pandemic, the RHI sub-study will be a single-arm, non-randomised trial in patients with MCI and hearing loss, who will receive a remotely delivered hearing intervention over 4 weeks.

Trial duration per participant:	6 months for intervention delivery and follow-up in TACT. The RHI sub-study during COVID-19 pandemic will last 4 weeks per participant.
Estimated total trial duration:	24 months
Planned trial sites:	Single-site
Total number of participants planned:	76 for TACT During the COVID-19 pandemic, we aim to recruit 12 participants to RHI sub-study.
Main inclusion/exclusion criteria:	Participants will be 55 years of age or older, with a diagnosis of MCI, and with mild to moderate adult-onset hearing loss, community-dwelling, without any self-reported hearing aid use in the past month.

For the single-arm Remote Hearing Intervention sub-study during the COVID-19 pandemic, we will invite those participants that had been consented for the randomised trial prior to the onset of COVID-19 who either (a) completed the healthy ageing intervention and are not using hearing aids; or (b) were included in the trial but could not complete their allocated intervention due to the onset of COVID-19.

Statistical methodology and analysis:

The main feasibility questions that the pilot aims to answer are: (a) is the trial feasible, in the sense of resulting in sufficiently high recruitment and sufficiently low dropout (retention); (b) are the interventions and schedule of assessments deliverable and acceptable to participants; (c) we will estimate the difference in hearing aid use at 6 months between the hearing intervention and healthy ageing intervention arms to inform sample size estimates for the future trial. We are including cognitive outcomes to assess their feasibility and acceptability, and to provide estimates including standard deviation to be used in the sample size calculation for the full trial. Only descriptive analysis will be reported. We will also conduct qualitative assessment of the interventions acceptability.

Prior to the onset of COVID-19, we randomised and obtained complete data for n=36 participants, confirming recruitment and retention (primary objective). These data will also allow us to address the questions (b-c) above.

During the COVID-19 pandemic, we will test the feasibility and acceptability of a remote version of the hearing aid intervention.

3 Background and Rationale

Hearing loss and cognition

[figure not shown]
It is a new finding that hearing loss is a risk factor for subsequent dementia. Studies have recruited people aged 50 to 70 years old without dementia, measured their hearing, and followed them for up to 20 years. People with hearing loss developed dementia at nearly double the rate of people with unimpaired hearing [1]. The mechanisms for this elevated risk are unknown, but they are likely to include direct detrimental effects of hearing loss on cognitive load and the amount of cognitive effort required from the brain to meet the challenges of daily life [2]. People with hearing loss are also at increased risk of depression and social isolation, which may be an intermediate step towards dementia [3]. Long term hearing loss is associated with accelerated brain atrophy, which is the biological marker with the strongest association to dementia [4].

Hearing loss affects 2 out of 3 people over 65 in the UK [5], but most of the people who in theory would benefit from a hearing aid never get one. Even when hearing aids are prescribed, up to half of people stop using them after a short time, particularly if they have memory problems [6].

Hearing aids and dementia prevention

Untreated hearing loss may be a missed opportunity to delay and prevent dementia in a substantial number of people. Figure 1 shows the putative mechanisms whereby hearing aid use may reduce dementia risk.

Figure 1. Hypothetical pathway to dementia that could be treated with hearing aid use

Hearing aid provision is the first-line clinical intervention for adults with mild to moderate hearing loss, which constitute the vast majority of people with this condition. Hearing aids are safe, and effective at improving hearing-specific health-related quality of life, general health-related quality of life and listening ability [7]. There is some evidence that hearing aid use may improve cognitive performance immediately after fitting [8], and continuing after 4 months of use [9]. It is unknown whether these benefits of treating hearing loss on cognitive performance persist and if they translate into reduced cognitive and functional decline over time, which is key to achieving reduction in dementia risk. The only way to find out if hearing aids can help to delay dementia is to run a randomised controlled clinical trial to directly compare the effect of using hearing aids, as against usual care, on the risk of developing dementia. Such a trial has not been conducted before.

In the United States, our collaborator [name] is conducting the ACHIEVE trial [10], which will be assessing the effect of hearing aid use on cognitive decline in a cognitively healthy population. In our trial, we have chosen people with mild cognitive impairment (MCI) as our trial population, because people with MCI are at much higher risk of dementia (approximately 15% incidence of dementia per year, or 50% risk over 3 years) than the cognitively healthy population of the same age, so that any benefits of hearing aid treatment should be apparent within a relatively short trial period. Recruiting participants with cognitive impairment brings additional challenges, in particular it will be more difficult for our participants than for cognitively healthy subjects to learn to use the hearing aids and remember to use them regularly. Our intervention design, with home-based assessments and integration with daily routine, will address these specific obstacles.

The anticipated fully-sized trial will be powered to identify differences in cognitive decline between those allocated to an interventional arm of supported hearing aid use versus a healthy ageing intervention in the MCI population. The current project will perform preparatory work for this future full-sized trial addressing the difficulties that this future trial faces to be successful. The definitions of pilot and feasibility randomised studies used in this document are as per CONSORT statement [11].

Addressing the challenges raised by COVID-19 Pandemic

COVID-19 is a grave global challenge for public health. It is also a challenge for clinical trials, especially those relying on face-to-face delivery of interventions, such as TACT. This has been recognised by

funders and regulatory agencies. In the following we have followed recent guidance on how to restart trials safely ^{1,2}.

For TACT, the main challenge is ensuring the safety of participants. Participants are aged 55 and over, so they are at higher risk from COVID-19 complications; some of our participants are in the high-risk category and shielding. The initial home-based hearing aid and support intervention would therefore not be suitable as it could put participants at increased risk of contracting the virus. This is a challenge also faced by NHS audiological cases, which have been paused during the epidemic except for urgent audiological treatment. Hearing aid provision and support is not an urgent treatment. However, given that in the absence of a vaccine social distancing for vulnerable populations may be maintained for months or years, it is important that Remote Hearing Interventions for audiological care are developed and tested, with a view to potential dementia prevention in the MCI population. Effective hearing aid treatment is likely to be particularly important during the pandemic as the measures in place to prevent the spread of the virus, such as social distancing and face coverings or masks, will have a disproportionate detrimental impact in those people with impaired hearing, who often rely on lip reading for communication. We will therefore test the feasibility and acceptability of a Remote Hearing Intervention during the COVID-19 pandemic.

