During the COVID-19 pandemic, and in keeping with the overall primary objective, the study will be a single-arm, non-randomised trial piloting a remotely delivered version of the active intervention of early hearing aid provision and support to test recruitment, feasibility and acceptability .

5 Trial design

The trial is a randomised controlled pilot trial. 76 participants with mild cognitive impairment and hearing loss will be randomised on a 1:1 ratio to the TACT Hearing Intervention of home-based hearing assessment, timely hearing aid fitting, and psychological and practical support to sustain adherence to treatment, versus a Healthy Ageing Intervention (HAI), whereby the participant will be given information about their hearing impairment and advised to consult with their GP to obtain NHS audiological treatment, as well as being provided with one-to-one sessions with a researcher (matching the intensity of social contact of the Hearing Intervention) on behavioural changes that can promote healthy ageing and may reduce risk of progression from MCI to dementia.

Participants for the pilot trial will be aged 55 years or above and recruited from memory clinics with a diagnosis of mild cognitive impairment, who have evidence of hearing loss as per audiologist

[figure not shown]
assessment, and who are willing to be treated with hearing aids if appropriate following audiology assessment. Assessments will take place in people's homes. Figure 3 presents the expected flow of participants through the trial.

The duration of follow-up in this pilot trial will be 6 months. People who abandon hearing aid use do so shortly after starting treatment, typically during the first few weeks of being fitted with aids. Conversely, there is evidence that behavioural health change, when sustained for 6 months or more is likely to be permanent [15], and therefore that adherence to hearing aids at trial end is likely to provide a valid estimate of longer term compliance. It is expected that participants allocated to the Hearing Intervention will be able to sustain adherence to hearing aids. The trial objective of 70% adherence to hearing aids treatment in the hearing intervention at 6 months, if met, will be a strong indicator that adherence is solidly established and that a longer duration definitive trial is feasible. We envisage the duration of a fully-powered trial to be 2 to 3 years.

Non-blinding of assessors

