 - (a) Potential participants will be excluded if hearing aids were prescribed in the past three months, irrespective of their use; however, we will contact these potential participants again after 3 months following prescription of their hearing aids and they will be eligible if they report no or low use of hearing aids. Low use is defined as less than 2 hours per day on average over the past 7 days (when at home and in usual health).
 - (b) Participants determined to have occluding cerumen as per otoscopy. These participants may be enrolled after cerumen removal. We will advise participants with occluding cerumen to access accredited cerumen removal services, following recent NICE guidelines (<https://cks.nice.org.uk/earwax>, and "Hearing loss in adults: assessment and management"; NICE Guideline, June 2018 [NG98]). Participants who are identified as needing cerumen removal will be advised to consult their GP to arrange cerumen removal. They will also be offered reimbursement if they choose to have privately arranged cerumen removal by an accredited provider instead. If practicable, and at the discretion of the trial audiologist, participants may also be offered cerumen removal by the trial audiologist, who has undergone necessary training for cerumen removal procedures.

6.1.3 Eligibility criteria for participants for the Remote Hearing Intervention sub-study (COVID-19)

1. For the single-arm Remote Hearing Intervention sub-study during COVID-19 pandemic, we will invite those participants that had been consented for the randomised trial prior to the onset of COVID-19, therefore meeting the inclusion and exclusion criteria at the time they consented to participate in TACT, and who either
 - (a) completed the healthy ageing intervention and are not using hearing aids; or
 - (b) were included in the trial but not could not complete their allocated intervention due to the onset of COVID-19.
2. Potential participants will be excluded if in the opinion of the research team, would be unable to complete remote procedures.
3. Potential participants will be excluded if they report any new ear pain or discharge or any audiological symptoms that would require face to face audiological assessment prior to inclusion.

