11.3 Sample size calculation

This pilot trial will assess the feasibility of proceeding to the future definitive RCT of sufficient duration to detect differences in cognitive changes between arms. The main feasibility questions that the pilot aims to answer are: (a) is the trial feasible, in the sense of resulting in sufficiently high recruitment, randomisation and sufficiently low dropout at 6 months; (b) is the Hearing Intervention deliverable and acceptable to participants; (c) estimate the difference in hearing aid use at 6 months between the Hearing Intervention and Healthy Ageing Intervention arms to inform sample size estimates for the future trial. We are including cognitive outcomes to assess their feasibility and acceptability, and to provide estimates including standard deviation to be used in the sample size calculation for the full trial. As a feasibility study, the current trial is not powered to detect differences in the cognitive outcomes between the arms. Therefore, only descriptive analyses will be performed using the data collected. No formal power calculation is necessary, and instead the sample size has been determined as to provide sufficient precision (sufficiently narrow confidence intervals) for trial estimates of recruitment and randomisation, dropout, acceptability of the intervention, and difference in hearing aid usage between arms, as detailed below.

With 76 randomised participants, we will achieve the following 95% confidence intervals (CI) for our expected estimates of recruitment, randomisation, dropout, acceptability of the intervention, and difference in hearing aid adherence between the Hearing Intervention and Healthy Ageing Intervention at the end of trial [88]:

1. Recruitment and randomisation of eligible participants with a MCI diagnosis from NHS community memory clinics. Target: 50% of eligible participants will be randomised; with n=76 recruited subjects the 95% CI would be [39-61].
2. Follow-up: target of 80% randomised participants with complete follow-up at 6 months,

95%CI with n=76 would be [71-89].

3. Acceptability of the Hearing Intervention: proportion of participants allocated to the Hearing Intervention completing ≥ 2 intervention sessions – expected value $\geq 80\%$ of intervention group, 95% CI with n=76 would be [71-89].

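### Section 2 treats recruitment and retention as confirmed by 36 participants with complete data, but gives no denominators, and 36 do not carry the precision stated for 76

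*Protocol*

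**What the plan says.** **Status in section 2 (Summary, statistical methodology).** Before COVID-19, "we randomised and obtained complete data for n=36 participants, confirming recruitment and retention (primary objective". The next sentence says these data will also serve questions (b), deliverability and acceptability, and (c), the difference in hearing aid use at 6 months. No number eligible, screened or randomised appears with the 36.

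**Definitions.** Section 11.1 sets recruitment as a proportion of eligible participants. Section 11.6.2 divides the number randomised by the number screened. For retention, section 11.6.2 divides by all randomised, and section 11.3 has a "target of 80% randomised participants with complete follow-up at 6 months". Acceptability is defined within the Hearing Intervention arm only.

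**Planned size and precision.** Section 5 states that "76 participants with mild cognitive impairment and hearing loss will be randomised on a 1:1 ratio", and section 2 still lists 76 as planned. Section 11.3 begins "With 76 randomised participants, we will achieve the following 95% confidence intervals" and gives recruitment 50% [39-61], retention 80% [71-89], acceptability 80% [71-89] and a difference in use of 50 points [31-69]. The progression guidance uses these same ranges. A point estimate inside its range is a go signal, one up to 10% below the lower limit prompts a look at modifications, and anything lower is a signal not to progress.

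**Interrupted participants.** Section 6.1.3 opens the remote sub-study to people who "were included in the trial but not could not complete their allocated intervention due to the onset of COVID-19". Sections 2 and 6.3 repeat this category.

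**The concern.** Recruitment and retention belong to the primary objective. Each is a proportion, and a proportion cannot be confirmed from its numerator. The 36 are described by their having complete data, and the protocol itself describes a further group that was allocated but interrupted, so 36 cannot be taken as the number randomised.

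The precision is also at issue. The data that section 2 relies on number fewer than half of the 76 on which section 11.3 is built, and nothing in the protocol says what precision the smaller number gives. The Trial Steering Committee would go into the progression decision with a primary objective already recorded as met. It would also receive a difference in hearing aid use, meant to inform the main trial's sample size, whose uncertainty is larger than the protocol states.

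**Working it through.** **1. Reproduce section 11.3.** Inputs: 76 randomised 1:1, so 38 per arm; targets 50%, 80%, 80%; expected use 70% against 20% (section 11.2b). Formulas (Wald): p ± 1.96 × √(p(1−p)/n), and for the difference 1.96 × √([p₁(1−p₁) + p₂(1−p₂)]/n per arm).

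- Recruitment: 1.96 × √(0.25/76) = 11.2 points, giving 38.8 to 61.2.
- Retention: 1.96 × √(0.16/76) = 9.0 points, giving 71.0 to 89.0.
- Difference: 1.96 × √((0.21 + 0.16)/38) = 19.3 points, giving 30.7 to 69.3.

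These match the protocol. Acceptability matches only if n=76 is used. With its defined one-arm denominator of 38 the half-width is 12.7 points and the interval [67-93]. That is a separate error and is kept out of the comparison below.

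**2. The same formulas with the 36 relied on** (18 per arm is an assumption, since the protocol gives no split):

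| Endpoint | At planned size | At 36 |
|---|---|---|
| Retention 80% | 71.0 to 89.0 | 66.9 to 93.1 |
| Acceptability 80%, one arm | 67.3 to 92.7 (n=38) | 61.5 to 98.5 (n=18) |
| Difference 50 points | 30.7 to 69.3 | 21.9 to 78.1 |

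Every half-width grows by √(76/36) = 1.45.

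Recruitment depends on the denominator chosen. Taking n=36, as section 11.3 does with n=76, gives 33.7 to 66.3. With the eligible as denominator and a rate of 50%, 36 randomised implies 72 eligible and 38.5 to 61.5, while 76 randomised implies 152 and 42.1 to 57.9.

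**3. Were more than 36 randomised?** Randomisation takes place at the screening visit (sections 8.1 and 8.2), and an allocated intervention presupposes it. Session D is scheduled for weeks 9-10 (section 8.3), and the outcome visit for 6 months with a tolerance of 4 weeks (section 8.4). A participant whose intervention was cut short by the pandemic could not have had 6-month data before its onset, and so is not among the 36. Someone past session D but short of 6 months at that point would also be missing from the 36.

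**4. Retention as 36/N, with N the unknown number randomised:**

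| N | 36/N | Exact 95% CI |
|---|---|---|
| 36 | 100% | 90.3 to 100 |
| 40 | 90.0% | 76.3 to 97.2 |
| 45 | 80.0% | 65.4 to 90.4 |
| 48 | 75.0% | 60.4 to 86.4 |
| 50 | 72.0% | 57.5 to 83.8 |
| 51 | 70.6% | 56.2 to 82.5 |
| 60 | 60.0% | 46.5 to 72.4 |

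The 80% target is met up to N=45. The estimate drops below the 71% go limit from N=51. At N=60 it is below 61%, the do-not-progress line if the 10% in section 11.3 means percentage points (71 − 10).

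**The case against.** Several stronger readings are tempting, and the documents do not support them.

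- **That the retention endpoint is circular.** The definition is sound, because section 11.6.2 divides by all randomised. Section 2 is a status note and does not change it. If exactly 36 had been randomised and all completed, retention would be 100%. The protocol does not say so, and the interrupted category points the other way, but that category is an eligibility criterion and not a count.
- **That retention has failed.** With 4, 8 or 12 participants beyond the 36, retention is 90%, 82% or 75%, and each is a go. It takes 15 or more to fall below 71%. People not yet due at 6 months when the pandemic began are also not dropouts in the ordinary sense.
- **That the trial closed at 36, so the planned precision is lost.** No section says randomisation is closed, and 76 is still listed as planned. The statement that no other new participants will be recruited concerns the sub-study. Section 11.3 is conditional on 76, and section 11.6.2 already calls for estimates with 95% CIs, which will show the precision achieved.
- **That the adherence interval reaches the stop line.** The lower bound of 22 lies close to 31 − 10 = 21, but the rule compares point estimates with fixed limits, not confidence bounds. Read as a relative 10%, the line would be 31 × 0.9 = 27.9.
- **That acceptability falls from [71-89] to [62-98].** Part of that gap is the one-arm denominator error. The loss from fewer participants is from [67-93] to [62-98].

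It is also fair to say that this is a descriptive pilot, that the limits are guidance, and that the steering committee decides after the trial ends. What remains is that section 2 declares a primary objective met on a count that cannot show it, and relies on 36 participants while the only stated precision is for 76.

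**Conclusion.** The concern holds in this limited form. The 36 are a numerator without the denominators that sections 11.1 and 11.6.2 require, so neither recruitment nor retention can be called confirmed from what section 2 gives. The missing number matters for a primary endpoint: anywhere from 36 to 45 randomised meets the 80% target, and 51 or more falls below the go limit.

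The data named for questions (b) and (c) give intervals about 1.45 times as wide as the planned size would. The lower end falls by about 4 points for retention and 9 points for the difference in use.

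This rests on Wald intervals, which reproduce the protocol's figures, on an assumed 18 per arm, and on a range for N because the number randomised is not stated. If N lies above 36, the retention interval is somewhat narrower than at 36; at N=45 and 80% it is 68 to 92. It does not follow that retention was poor, that its definition is flawed, or that the trial stopped at 36.

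**What to change.** - **Section 2:** replace the claim that recruitment and retention are confirmed with the numbers eligible, screened, randomised per arm, due at 6 months and completed, and with the resulting estimates and their 95% CIs.
- **Retention:** report it over all randomised, as section 11.6.2 defines it. Add a second estimate limited to participants whose 6-month visit fell due before the pandemic, so that interruption and dropout can be told apart.
- **Section 11.3:** add the expected precision at the number actually randomised as a separate statement, with acceptability based on the Hearing Intervention arm alone. Keep the go/stop limits at their pre-specified values. Recalculating those ranges at 36 would lower the go limit for retention from 71 to 67 and for the difference from 31 to 22 after data are in hand.

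The cost is wording and counts that the trial team should already hold. The drawback is that the stated precision becomes less favourable.
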